Appendix C. Pediatric Ulcerative Colitis Activity Index (PUCAI)

Item	Points
1. Abdominal pain	
No pain	0
Pain can be ignored	5
Pain cannot be ignored	10
2. Rectal bleeding	
None	0
Small amount only, in < 50% of stools	10
Small amount with most stools	20
Large amount (> 50% of stool content)	30
3. Stool consistency of most stools	
Formed	0
Partially formed	5
Completely unformed	10
4. Number of stools per 24 hours	
0-2	0
3-5	5
6-8	10
> 8	15
5. Nocturnal stools (any episode causing wakening)	
No.	0
Yes	10
6. Activity level	
No limitation of activity	0
Occasional limitation of activity	5
Severe restricted activity	10
TOTAL MAXIMUM SCORE	85

The Pediatric Ulcerative Colitis Activity Index (PUCAI)²³ is the copyright of The Hospital for Sick Children, Toronto, Canada, authored by [name], [name] and [name]. The PUCAI will be provided under license from The Hospital for Sick Children and must not be copied, distributed or used in any way without the prior written consent of The Hospital for Sick Children.

Appendix D. Mayo Scoring System

The Mayo Score is a composite of the following subscores: Stool Frequency subscore, Rectal Bleeding subscore, Endoscopic appearance subscore, and Physician's Global Assessment subscore.

Stool Frequency Subscore

- 0 = Normal
- 1 = 1 2 stools/day more than normal
- 2 = 3 4 stools/day more than normal
- 3 = > 4 stools/day more than normal

Each subject serves as his or her own control to establish normal stool frequency and the degree of abnormal stool frequency.

Rectal Bleeding Subscore

- 0 = None
- 1 = Visible blood with stool less than half the time
- 2 = Visible blood with stool half of the time or more
- 3 =Passing blood alone

A score of 3 for bleeding requires subjects to have at least 50% of bowel motions accompanied by visible blood and at least one bowel motion with blood alone.

Endoscopy Subscore:

[figure not shown]
- 0 = Normal or inactive disease
- 1 = Mild disease (erythema, decreased vascular pattern, mild friability)
- 2 = Moderate disease (marked erythema, absent vascular pattern, friability, erosions)
- 3 = Severe disease (spontaneous bleeding, ulceration)

Physician's Global Assessment Subscore

- 0 = Normal
- 1 = Mild disease
- 2 = Moderate disease
- 3 =Severe disease

The physician's global assessment acknowledges the three other subscores, the subject's daily record of abdominal discomfort and functional assessment, and other observations such as physical findings, and the subject's performance status.

Adapted from Schroeder KW, et al, and Lewis JD, et al. 24,25

Script for Collection of Mayo Scores

The Mayo Score is a composite of the following subscores: Stool Frequency subscore, Rectal Bleeding subscore, Endoscopy subscore, and Physician's Global Assessment subscore.

The Partial Mayo Score is a composite of the following subscores: Stool Frequency subscore, Rectal Bleeding subscore, and Physician's Global Assessment subscore.

[figure not shown]
Stool Frequency Subscore

The stool frequency subscore is calculated by comparing the stool frequency to a normal number of bowel movements. The normal number of bowel movements is the number of stools per day (24 hours) that is typical for the subject when having active UC but not experiencing a flare and needs to be designated once prior to enrollment. The normal number of bowel movements should represent a full number of at least 1.

Subjects will record the daily number of stools throughout the trial. Using these numbers, the Stool Frequency subscore will be assessed for each study day as follows:

- A number of bowel movements lower than or equal to the normal number of bowel movements should be scored as 0 = Normal.
- One or 2 bowel movements more than the normal number of bowel movements should be scored as 1.
- Three or 4 bowel movements more than the normal number of bowel movements should be scored as 2.
- Five or more bowel movements more than the normal number of bowel movements should be scored as 3.

The Stool Frequency subscores from the 5 days prior to each study visit will be averaged and used for the Stool Frequency subscore for each study visit. In order to account for unavailable or excluded diary entries as per the provisions given below diary entries of the most recent 5 days within 14 days prior to each study visit will be used.

The Stool Frequency subscore during days which the subject received anti-diarrheal medication will be scored as a 3. Diary entries for stool frequency should not be included in the 5 days prior to the visit that are evaluated for the Stool Frequency subscore for the following days: (1) the day the subject received medication for bowel preparation prior to endoscopy, (2) the day the subject underwent an endoscopy, and (3) 2 days following the endoscopy. Earlier diary entries will be used accordingly in order to provide the most recent data for 5 days prior to the respective study visit.

[figure not shown]
Rectal Bleeding Subscore

Subjects should record a daily rectal bleeding subscore value as follows:

- No visible blood with stool during the respective day should be scored as 0.
- Visible blood with stool less than half the time during the respective day should be scored as 1.
- Visible blood with stool at least half the time during the respective day should be scored as 2.
- A score of 3 for bleeding requires subjects to have at least 50% of bowel motions accompanied by visible blood and at least one bowel motion with blood alone.

The score entries into subject's diary from the 5 days prior to each study visit will be averaged and used for the Rectal Bleeding subscore for each study visit. In order to account for unavailable or excluded diary entries as per the provisions given below diary entries of the most recent 5 days within 14 days prior to each study visit will be used.

Diary entries for rectal bleeding should not be included in the 5 days prior to the visit that are evaluated for the Rectal Bleeding subscore for the following days: (1) the day the subject received medication for bowel preparation prior to endoscopy, (2) the day the subject underwent an endoscopy, and (3) 2 days following the endoscopy. Earlier diary entries will be used accordingly in order to provide the most recent data for 5 days prior to the respective study visit.

Physician's Global Assessment Subscore

The physician's global assessment acknowledges the 2 subject-reported subscores, the endoscopy subscore as applicable, the subject's daily record of abdominal discomfort and functional assessment during the 5 days prior to the visit, and other observations such as physical findings, and the subject's performance status in order to assess disease activity as follows:

- \bullet 0 = Normal
- 1 = Mild disease
- 2 = Moderate disease
- 3 =Severe disease

[figure not shown]
Endoscopy Subscore

The endoscopist should evaluate each observed segment of the colon (rectum, sigmoid, descending colon, transverse colon, ascending colon/cecum) by using the classification as follows:

- 0 = Normal or inactive disease
- 1 = Mild disease (erythema, decreased vascular pattern, mild friability)
- 2 = Moderate disease (marked erythema, absent vascular pattern, friability, erosions)
- 3 = Severe disease (spontaneous bleeding, ulceration)

The endoscopic subscore for the subject will be the worst score of the observed segments.

[figure not shown]
The local endoscopist should also separately assess presence or absence of friability (yes/no).

Appendix E. Work Productivity and Activity Impairment Questionnaire: Ulcerative Colitis V2.0 (WPAI: UC) – Caregiver

The following questions ask about the effect of your child's ulcerative colitis on your ability to work and perform regular activities. Please fill in the blanks or circle a number, as indicated.

•	licated.
1.	Are you currently employed (working for pay)? NO YES
	If NO, check "NO" and skip to question 6.
	The next questions are about the past 7 days, not including today.
2.	During the past 7 days, how many hours did you miss from work because of problems associated with your child's ulcerative colitis? Include hours you missed on sick days, times you went in late, left early, etc., because of your child's ulcerative colitis. Do not include time you missed for your child to participate in this study.
	HOURS
3.	During the past 7 days, how many hours did you miss from work because of any other reason, such as vacation, holidays, time off for your child to participate in this study?
	HOURS
4.	During the past 7 days, how many hours did you actually work?
	HOURS (If "0," skip to question 6.)
5.	During the past 7 days, how much did your child's ulcerative colitis affect your productivity while you were working?
	Think about days you were limited in the amount or kind of work you could do, days you accomplished less than you would like, or days you could not do your work as carefully as usual. If your child's ulcerative colitis affected your work only

a little, choose a low number. Choose a high number if your child's ulcerative colitis affected your work a great deal.

[figure not shown]
Consider only how much your child's ulcerative colitis affected productivity while you were working.

My child's Ulcerative colitis had _												My child's Ulcerative colitis completely
no effect on my work	0	1	2	3	4	5	6	7	8	9	10	prevented me from working

CIRCLE A NUMBER

6. During the past 7 days, how much did your child's ulcerative colitis affect your ability to do your regular daily activities, other than work at a job?

By regular activities, we mean the usual activities you do, such as work around the house, shopping, childcare, exercising, studying, etc. Think about times you were limited in the amount or kind of activities you could do and times you accomplished less than you would like. If your child's ulcerative colitis affected your activities only a little, choose a low number. Choose a high number if your child's ulcerative colitis affected your activities a great deal.

[figure not shown]

Consider only how much your child's ulcerative colitis affected your ability to do your regular daily activities, other than work at a job.

My child's Ulcerative colitis had no effect												My child's Ulcerative colitis completely prevented
on my daily activities	0	1	2	3	4	5	6	7	8	9	10	me from doing my daily activities

CIRCLE A NUMBER

WPAI:UC - Caregiver V2.0 (US English)

[figure not shown]
Appendix F. Body Weight Adjusted Volumes of Study Drug for Administration of Open Label Adalimumab 0.6 mg/kg Dosing (Weight Based)

Weight (kg)	Administered (# of vial used)	Volume (mL)	Weight (Kg)	Administered (# of vial used)	Volume (mL)	Weight (kg)	Administered (# of vial used)	Volume (mL)
14	1×	0.17	36	1 x	0.43	58	1×	0.70
15	1×	0.18	37	1 x	0.44	59	1×	0.71
16	1×	0.19	38	1 x	0.46	60	1×	0.72
17	1×	0.20	39	1 x	0.47	61	1×	0.73
18	1×	0.22	40	1 x	0.48	62	1×	0.74
19	1×	0.23	41	1 x	0.49	63	1×	0.76
20	1×	0.24	42	1 x	0.50	64	1×	0.77
21	1×	0.25	43	1 x	0.52	65	1×	0.78
22	1×	0.26	44	1 x	0.53	66	1×	0.79
23	1×	0.28	45	1 x	0.54	67	1×	0.80
24	1×	0.29	46	1 x	0.55	68	1×	0.80
25	1×	0.30	47	1 x	0.56	69	1×	0.80
26	1×	0.31	48	1 x	0.58	70	1×	0.80
27	1×	0.32	49	1 x	0.59	71	1×	0.80
28	1×	0.34	50	1 x	0.60	72	1×	0.80
29	1×	0.35	51	1 x	0.61	73	1×	0.80
30	1×	0.36	52	1 x	0.62	74	1×	0.80
31	1×	0.37	53	1 x	0.64	75	1×	0.80
32	1×	0.38	54	1 x	0.65	76	1×	0.80
33	1×	0.40	55	1 x	0.66	77	1×	0.80
34	1×	0.41	56	1 x	0.67	78	1×	0.80
35	1×	0.42	57	1 x	0.68	79	1×	0.80
						80	1×	0.80

[figure not shown]
Adalimumab
M10-870 Protocol Amendment 5 EudraCT 2015-001346-29

Appendix G.	70-Day Follow-Up Call – Sample
Site Name/Number:	
Subject Number:	
Please contact subj	ects who discontinue adalimumab 70 days following study drug discontinuation.
Date of Call:	
	low-up (Please check this box if subject was not willing to provide any follow-up or you were unable to speak to the subject following at least three attempts.) Reported
was last seen in clir	events (AE) and/or Serious Adverse Events (SAE) that occurred since the subject nic for this study. If needed, provide AE/SAE details on the AE worksheet report all SAEs to AbbVie within 24 hours of being made aware of the event.)
_	

Appendix H. Non-Drug Materials Provided to the Study Sites

[figure not shown]
Study sites will receive the following supplies prior to or during the study for distribution to subjects:
Tote Bags
Coolers
Gel Packs
Subject Diaries
Sharps Containers

Appendix I. Measurements and Volume(s) of Blood Samples to Be Drawn

The measurements and volume(s) of blood samples to be drawn at the time point indicated in the table below:

Visit	Measurement	Volume (mL)	Total Blood Volume (mL)/Visit
Baseline samples	Chemistry, hCG*, hsCRP	2.5	7.5**
Drawn at	Hematology	2.0	
Week 52 Study M11-290			
	QuantiFERON TB Gold	3.0	
Week 4	Chemistry, hCG*	2.5	4.5
	Hematology	2.0	
Week 8	hCG*	2.5	2.5
Week 12	Chemistry, hCG*	2.5	4.5
	Hematology	2.0	
Week 24	Chemistry, hCG*, hsCRP	2.5	4.5
	Hematology	2.0	
Week 36	Chemistry, hCG*,	2.5	4.5
	Hematology	2.0	
Week 48	Chemistry, hCG*, hsCRP	2.5	
	Hematology	2.0	7.5
	QuantiFERON TB Gold^	3.0	
Week 60	Chemistry, hCG*	2.5	4.5
	Hematology	2.0	
Week 72	Chemistry, hCG*, hsCRP	2.5	4.5
	Hematology	2.0	
Week 84	Chemistry, hCG*	2.5	4.5
	Hematology	2.0	
Week 96	Chemistry, hCG*, hsCRP	2.5	
	Hematology	2.0	7.5
	QuantiFERON TB Gold^	3.0	
Week 108	Chemistry, hCG*,	2.5	4.5
	Hematology	2.0	

Visit	Measurement	Volume (mL)	Total Blood Volume (mL)/Visit
Week 120	Chemistry, hCG*, hsCRP	2.5	
	Hematology	2.0	4.5
Week 144	Chemistry, hCG*, hsCRP	2.5	
	Hematology	2.0	7.5
	QuantiFERON TB Gold^	3.0	
Week 168	Chemistry, hCG*, hsCRP	2.5	4.5
	Hematology	2.0	
Week 192	Chemistry, hCG*, hsCRP	2.5	
	Hematology	2.0	7.5
	QuantiFERON TB Gold^	3.0	
Week 216	Chemistry, hCG*, hsCRP	2.5	4.5
	Hematology	2.0	
Week 240	Chemistry, hCG*, hsCRP	2.5	
	Hematology	2.0	7.5
	QuantiFERON TB Gold^	3.0	
Week 264	Chemistry, hCG*, hsCRP	2.5	4.5
	Hematology	2.0	
Week 288/ Premature	Chemistry, hCG*, hsCRP	2.5	
Discontinuation	Hematology	2.0	7.5
	QuantiFERON TB Gold^	3.0	
Unscheduled Visit	Chemistry, hCG*, hsCRP	2.5	
	Hematology	2.0	4.5
	Total		101.5

^{*} Only performed in female of childbearing potential that has positive urine pregnancy test.

^{**} At the Baseline visit, the blood samples for Study M10-870 will be completed as part of Week 52 of the Study M11-290 protocol and blood volume is not used to calculate the total blood volume for Study M10-870.

[^] Subjects will not have the QuantiFERON test performed if a PPD test is used. For subjects with a negative TB test, a TB test will be required at Week 48, 96, 144, 192, 240 and 288. An annual TB screen testing will not be required for subjects who have been treated for latent or active TB or have had a positive TB test at any time (prior to the study, or testing performed at any time point during the Study M11-290).

3.0 Introduction

This statistical analysis plan (SAP) will provide details to further elaborate statistical methods as outlined in the protocol of Study M10-870, "A Multi-Center, Open-Label Study of the Human Anti-TNF Monoclonal Antibody Adalimumab to Evaluate Long-Term Safety and Tolerability of Repeated Administration of Adalimumab in Pediatric Subjects with Ulcerative Colitis Who Completed the Study M11-290" and describe analysis conventions to guide the statistical programming work. The analysis plan is based on the study protocol Amendment 3 dated 30 July 2019.

The analyses for the Japan Sub-Study will be described in a separate SAP. All described analysis in this SAP will be for subjects enrolled outside of Japan.

The statistical analysis will be performed using the SAS® software version 9.2 or later.

4.0 Study Objectives, Design and Procedures

[figure not shown]
4.1 Objectives

The objective of the study is to evaluate the long-term safety, tolerability, and maintenance of clinical response, of repeated administration of adalimumab (ADA) administered subcutaneously (SC) in pediatric subjects with ulcerative colitis (UC) who participated in, and successfully completed, Protocol Study M11-290 through Week 52.

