8.0 Statistical Methods and Determination of Sample Size

8.1 Statistical and Analytical Plans

The objectives of the statistical analyses are to evaluate the efficacy and safety of adalimumab for the maintenance of clinical remission in pediatric subjects with moderately to severely active ulcerative colitis. Complete, specific details of the

statistical analysis will be described and fully documented in the Statistical Analysis Plan (SAP). The SAP will be finalized prior to the database lock.

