5.0 Analysis Populations

5.1 Definition for Analysis Populations

[figure not shown]
The Full Analysis Set will be used for all analyses and includes all subjects who received at least one dose of ADA in Study M10-870.

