2. PUCAI

Pediatric Ulcerative Colitis Activity Index (PUCAI) is calculated as the sum of six subscores [each being a 2 day average, see above] of PUCAI (abdominal pain [no pain = 0, pain can be ignored = 5, pain cannot be ignored = 10], rectal bleeding [none = 0, small amount with < 50% of stools = 10, small amount with most stools = 20, large amount with > 50% of stool content = 30], stool consistency of most stools [formed = 0, partially formed = 5, completely unformed = 10], number of stools per 24 hours [0 to 2 = 0, 3 to 5 = 5, 6 to 8 = 10, > 8 = 15], nocturnal stools [no = 0, yes = 10], activity level [no limitation = 0, occasionally limited = 5, severe restriction = 10]) with maximum total score 85. Higher scores represent more severe disease.

- PUCAI remission is defined as PUCAI < 10.
- PUCAI response is defined as a decrease in PUCAI ≥ 20 points from Study M11-290-Baseline.

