10.2 Efficacy Analysis

The efficacy endpoints are:

- The proportion of subjects who achieve clinical remission as measured by PMS (defined as a PMS ≤ 2 and no individual subscore ≥ 1) over time;
- The proportion of subjects who achieve clinical response as measured by PMS (defined as a decrease in PMS ≥ 2 points and ≥ 30% from Study M11-290-Baseline) over time;
- The proportion of subjects who achieve PUCAI remission (defined as < 10) over time;
- The proportion of subjects who achieve PUCAI response (defined as a decrease in PUCAI ≥ 20 points from Study M11-290-Baseline).
- Change from Baseline in total IMPACT III Quality of Life score and subscores over time for subjects at least 9 years old at Baseline;
- Change from Baseline in WPAI scores over time;
- Change from Baseline in "z" scores for height over time;
- Change from Baseline in BMI over time;
- Change from Baseline in "z" scores for weight-for-age over time;
- Change from Baseline in albumin and total protein over time;
- Change from Baseline in hemoglobin, hematocrit, red blood cell count over time;
- Change from Baseline in hs-CRP levels over time;
- Proportion of subjects at appropriate Tanner stage (see Section 6.0) over time;
- Proportion of subjects in Mayo score clinical response over time (for subjects with available Mayo score);
- Proportion of subjects in Mayo score clinical remission over time (for subjects with available Mayo score);
- Proportion of subjects who achieve mucosal healing over time as measured by Mayo endoscopy subscore (defined as ≤ 1, for subjects with available Mayo score)
- Proportion of subjects in 9 point Mayo score (without PGA) clinical remission over time (for subjects with available Mayo score);

• Proportion of subjects in 6 point Mayo score (without PGA and endoscopy subscore) clinical remission over time (for subjects with available Mayo score).

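### The objective is maintenance of response, but no response or remission endpoint is conditioned on status at M10-870 Baseline, so maintenance is not directly estimated

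*SAP*

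**What the plan says.** **Objective.** Besides safety and tolerability, SAP Section 4.1 (like Protocol Section 4.0) names the "maintenance of clinical response, of repeated administration of adalimumab". Protocol Section 8.1, on the purpose of the statistical analyses, instead names the "maintenance of clinical remission in pediatric subjects with moderately to severely active ulcerative colitis".

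**Endpoints and denominators.** SAP Section 5.1 states: "The Full Analysis Set will be used for all analyses and includes all subjects who received at least one dose of ADA in Study M10-870". SAP Section 10.2 then lists "The proportion of subjects who achieve clinical response as measured by PMS" and "The proportion of subjects who achieve PUCAI response", together with PMS and PUCAI remission. The Mayo-based endpoints (response, remission, mucosal healing, and the 9-point and 6-point versions) are limited to subjects with an available Mayo score. No endpoint is limited by status at Week 0, which SAP Section 6.0 sets at the Week 52 visit of M11-290.

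**Reference point for response.** SAP Section 6.0 states: "PUCAI response is defined as a decrease in PUCAI ≥ 20 points from Study M11-290-Baseline". PMS response uses the same reference (SAP Table 2, Protocol Section 5.3.2). Response status at Week 0 can therefore be derived.

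**Missing data.** SAP Section 10.1 uses observed cases (OC) and last observation carried forward (LOCF). Protocol Section 8.1.4 plans observed data and non-responder imputation (NRI) at each visit, with LOCF for the last visit only.

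**Other analyses.** None of the subgroups in SAP Section 10.5 is defined by response or remission at Week 0, and SAP Section 10.4 names no sensitivity analysis.

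**The concern.** To maintain a response is to keep one already held. The natural estimate is the share of Week 0 responders who are still responders later. The planned proportions instead count everyone in response at a visit, whether the response was kept or is new.

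The two groups can be expected to mix. Protocol Section 5.2.1 requires completion of M11-290, not response. The flare criteria in Protocol Section 5.1 provide for Baseline PMS of 3 to 4 and 5 to 6, above the remission limit of 2. The plan thus foresees Week 0 non-remitters who may later remit, and it does not exclude Week 0 non-responders.

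A flat curve could then mean that nearly every responder kept the response, or that losses were balanced by gains. OC adds a second route: SAP Section 4.2 has subjects with persistently uncontrolled disease at the maximum dose leave the study, after which they drop out of the OC denominator.

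**Working it through.** The plan gives no figure on this point to reproduce: no expected responder share at Week 0 and no target maintenance rate. The only input from the documents is N = 55, the expected enrolment outside Japan (SAP Section 4.3). Counts at Week 0, losses and gains below are assumptions, shown as a range.

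**Step 1: identity.** Let R be the number of responders at Week 0, L the number of them not in response at a later visit, and G the number of Week 0 non-responders now in response. With all 55 observed, the planned proportion is (R − L + G)/55 and maintenance is (R − L)/R. The planned proportion is unchanged whenever L = G. Since G cannot exceed 55 − R, the largest loss an unchanged proportion can hide is min(R, 55 − R).

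**Step 2: range.** The last column assumes that about half of the non-responders gain response (14 of 27, 11 of 22, 8 of 16, 6 of 11, 2 of 5) and that an equal number of responders lose it.

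| Week 0 responders (assumed) | Planned proportion, unchanged | Largest hidden loss | Maintenance if about half of non-responders gain |
|---|---|---|---|
| 28 | 50.9% | 27 of 28 (96%) | 14/28 = 50.0% |
| 33 | 60.0% | 22 of 33 (67%) | 22/33 = 66.7% |
| 39 | 70.9% | 16 of 39 (41%) | 31/39 = 79.5% |
| 44 | 80.0% | 11 of 44 (25%) | 38/44 = 86.4% |
| 50 | 90.9% | 5 of 50 (10%) | 48/50 = 96.0% |
| 55 | 100% | none | 55/55 = 100% |

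The same identity applies to remission, with remitters in place of responders.

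**Step 3: effect of OC.** Assume 44 of 55 in response at Week 0, 11 of whom lose response and discontinue, while 5 of the 11 non-responders gain it.
- OC: (33 + 5)/(55 − 11) = 38/44 = 86.4%, above the 80.0% at Week 0.
- NRI: 38/55 = 69.1%.
- Maintenance, discontinuation counted as loss: 33/44 = 75.0%.

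LOCF would record these 11 as lost only if their last recorded value already showed the loss; a favourable last value would be carried on.

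**Step 4: precision of the conditional estimate.** At a proportion of 50%, the half-width is 1.96 × √(0.25/33) = 17.1 points with 33 subjects, against 1.96 × √(0.25/55) = 13.2 points with 55. Exact 95% intervals for the second row of the table are 48.2 to 82.0% for 22/33 and 45.9 to 73.0% for 33/55.

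**The case against.** The documents do not define maintenance. Because response is measured from M11-290 Baseline, the proportion in response over time shows whether the treated cohort still has the benefit gained since entering the parent study. That is a legitimate cohort-level reading.

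Some within-subject information is planned too. SAP Section 8.0 tabulates dose escalations, re-escalations after de-escalation, and reasons for discontinuation. Escalation follows a flare, and three of the four flare criteria compare the subject with his or her own M10-870 Baseline PMS.

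The study title also stresses safety and tolerability, all analyses are descriptive, and no error rate, power or sample size depends on this point.

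Most of this stands. A reader might infer that the planned tables say nothing about maintenance; the cohort-level proportions and the disposition tables show that this goes too far. They are still no substitute for a conditional proportion. Escalation is optional, and neither escalations nor discontinuations are tabulated by Week 0 status. A descriptive study should still describe what its objective names.

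**Conclusion.** The point holds in a limited form. No endpoint, subgroup or named sensitivity analysis estimates how many subjects in response or remission at M10-870 Baseline remain so.

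The size is unknown because the Week 0 responder share is not given. The masking can be large if about 60% are responders at entry, is small near 90%, and is zero at 100%. These bounds assume 55 subjects, all observed.

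Two stronger readings are not supported:
- A reader might infer that every endpoint uses all treated subjects. The Mayo-based endpoints and the OC analysis do not. None of those restrictions selects Week 0 responders, however, so the gap remains.
- A reader might infer that loss of response will in fact be hidden. The documents show only that the planned proportions could not reveal it where gains offset losses.

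The difference between maintenance of response and of remission is one of wording, since both states are tabulated over time. This is a worthwhile, inexpensive addition; it does not invalidate the planned analyses.

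**What to change.** - In SAP Section 10.2 add, at each visit with a 95% confidence interval, the proportion still in PMS response among Week 0 PMS responders and still in PMS remission among Week 0 PMS remitters. Do the same for PUCAI response and remission.
- Analyse these by the NRI of Protocol Section 8.1.4 as well as by OC, so that premature discontinuation counts as loss.
- State a separate rule for subjects classed as completers before Week 288: those switched to adult care or commercial drug (SAP Section 8.0), and those whose termination visit follows notice that the study is concluding (Protocol Section 5.4.2). One option is to take them out of later denominators and show their number.
- Show gains among Week 0 non-responders and non-remitters separately.
- Align the objective in Protocol Sections 4.0 and 8.1 and SAP Section 4.1.
- Before classifying remitters, reconcile the PMS remission limit. It reads as no subscore above 1 in the Protocol synopsis and SAP Section 4.2, but as no subscore of 1 or more in Protocol Section 5.3.2, SAP Table 2 and SAP Section 10.2. This may be an artefact of reading the PDF.

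Week 0 PMS and PUCAI are already collected, so the cost is a few tables and no new data. The downside is the smaller denominator and the wider interval shown in Step 4 of the working.
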